2.3.2 Safety population

The safety population will be comprised of all patients who take at least one dose of randomized treatment, and will be analyzed as-treated (according to the treatment actually received). In addition:

- Randomized patients for whom it is unclear whether they took the study medication will be considered as treated and included in the safety population.
- For patients receiving more than one study treatment during the trial, the treatment group allocation for as-treated analysis will be the treatment group in which he/she is treated for longer.

2.4 STATISTICAL METHODS

2.4.1 Demographics and baseline characteristics

Continuous data will be summarized using the number of available data, mean, standard deviation (SD), median, minimum, and maximum for each treatment group. Categorical and ordinal data will be summarized using the number and percentage of patients in each treatment group.

Parameters will be summarized on the randomized population analyzed in the treatment group to which they were randomized. Analyses for the safety population will be included in the appendices if the size of the safety population is different (>10%) from the size of that in the primary analysis population for any treatment group.

Parameters described in [Section 2.1.1](#) will be summarized by treatment group and overall treatment groups using descriptive statistics.

P-values on demographic and baseline characteristic data will not be calculated.

No specific description of the safety parameters will be provided at baseline. If relevant, the baseline values will be described along with each safety analysis.

No specific description of the efficacy parameters will be provided at baseline. If relevant, the baseline values will be described along with each efficacy analysis.

2.4.2 Prior or concomitant medications

The prior and concomitant medications will be presented for the randomized population.

Medications will be summarized by treatment group according to the WHO-DD dictionary, considering the first digit of the anatomic category (ATC) class (anatomic category) and the first 3 digits of the ATC class (therapeutic category). All ATC codes corresponding to a medication will be summarized, and patients will be counted once in each ATC category (anatomic or therapeutic) linked to the medication. Therefore patients may be counted several time for the same medication.

The table for prior medications will be sorted by decreasing frequency of ATC followed by all other therapeutic classes based on the overall incidence across treatment groups. In case of equal frequency regarding ATCs, alphabetical order will be used.

The tables for concomitant and posttreatment medications will be sorted by decreasing frequency of ATC followed by all other therapeutic classes based on the incidence the overall incidence across treatment groups. In case of equal frequency regarding ATCs, alphabetical order will be used.

2.4.3 Extent of investigational medicinal product exposure and compliance

The extent of IMP exposure and compliance will be assessed and summarized by actual treatment within the safety population (Section 2.3.2).

2.4.3.1 Extent of investigational medicinal product exposure

The duration of exposure during the study will be the total number of days of administration of IMP, ignoring temporary drug discontinuation. It will be calculated as (Date of the last IMP administration – date of the first IMP administration) + 1. The exposure to IMP will be summarized categorically (counts and percentages) on the safety population. If appropriate, exposure will also be summarized by starting dose.

Insulin dose (total, basal, mealtime/bolus, ratio of basal to bolus insulin dose) will be calculated.

Baseline and end of treatment IMP doses are the total daily IMP dose taken on the day of randomization and the total daily IMP dose taken at the end of the study. See Section 2.5.3 for baseline and end of treatment IMP dose calculation when the dose on randomization or end of treatment is missing.

Baseline and end of treatment meal time insulin doses are the average daily dose 3 days prior to randomization and the average daily dose 3 days prior to the last administration of IMP.

Insulin dose (total daily dose (units, units/kg), basal, mealtime/bolus, ratio of basal to bolus insulin dose) will be descriptively summarized for absolute values and change from baseline to the end of treatment. Mean insulin doses will also be plotted over time.

2.4.3.2 Compliance

A given administration will be considered noncompliant if the patient did not take the planned dose of treatment as required by the protocol. Overall treatment compliance is defined as the actual number of days with at least one administration of IMP compared to the planned number of days with IMP administration during the open-label treatment periods up to treatment discontinuation.

Treatment compliance, above-planned and under-planned dosing percentages will be summarized descriptively (n, mean, SD, median, minimum, and maximum). The percentage of patients with compliance of <80% will be summarized. In addition, the number and percentage of patients with at least 1 above-planned dosing administration will be given, as well as the number and percentage of patients with 0, (0, 20%], and >20% under-planned dosing administrations. No imputation will be made for patients with missing or incomplete data.

2.4.4 Analyses of efficacy endpoints

2.4.4.1 Analysis of primary efficacy endpoint(s)

The percentage of time glucose in target range 70-180mg/dL (3.9–10mmol/l) during week 16 (obtained from CGM) will be calculated based from the denominator of total time with valid data. The criteria to evaluate baseline and Week 16 CGM data are in Section 2.1.3.

The evaluable assessment interval for the calculation will comprise of 24-hour periods during Week 16 for which there is sufficient non-missing data. In order to be evaluable for analysis, a patient needs at least 4 days of 24-hour data meeting this criterion and should not receive protocol prohibited medication.

The endpoint will be summarized by treatment group using mean, median, standard deviation, minimum and maximum.

Differences between treatment groups will be assessed using a generalized linear model with identity link, adjusting for key baseline characteristics (duration of diabetes, baseline BMI, age and baseline value) and randomization strata if model permits. If model does not converge, for example due to over 90% patients fall into the carbohydrate counting, the specific factors which cause non convergence may be dropped from the model. Adjusted mean estimates for each treatment group with standard errors, the adjusted estimate of treatment mean difference with standard error and a 95 % confidence interval for the treatment mean difference will be provided. The statistical test will be for superiority of Toujeo over Lantus, two-sided and at a 5% significance level.

2.4.4.2 Analyses of secondary efficacy endpoints

The main secondary efficacy endpoints.

The seven main secondary efficacy endpoints will be analyzed as below and tested sequentially after the primary endpoint. Testing strategy is described in 2.4.4.3

The incidence (proportion of patients with any nocturnal symptomatic hypoglycemia events) will be analyzed using logistic regression, adjusting for randomization strata and other baseline characteristics (duration of diabetes, baseline BMI and age) if the model permits.

The risk ratio (RR) of hypoglycemia of Toujeo versus Lantus will be assessed by a log-binomial regression model adjusting for randomization strata and other baseline characteristics (duration of diabetes, baseline BMI and age) if the model permits.

The rate (number of events per patient-year) of nocturnal symptomatic hypoglycemic events will be analyzed using an over-dispersed Poisson regression model, adjusting for randomization strata and other baseline characteristics (duration of diabetes, baseline BMI and age) if the model permits.

The mean change of each participant's glucose level during the last four hours of CGM data collection prior to next day basal insulin injection comparing Toujeo versus Lantus will be analyzed using a mixed model, in which treatment arm is a fixed categorical effect and patient is a random effect, adjusting for randomization strata and other baseline characteristics (duration of diabetes, baseline BMI and age) if the model permits. If a patient has more than 7 evaluable days of CGM data, only the first 7 days closest to Week 15 will be included.

The percentage of time glucose concentrations obtained by CGM within the target range of 70-140 mg/dL (3.9-7.8 mmol/L) during the last 4 hours of CGM data prior to the next day basal insulin injection will be summarized and analyzed by the same model as the primary endpoint.

Total, within day and between day standard deviation (SD) will also be summarized and analyzed by the same model as the primary efficacy endpoint.

Other endpoints

The total, within day and between day CV% and SD will be summarized at baseline and study endpoint by treatment group using mean, median, standard deviation, minimum and maximum, and will be analyzed as for the primary endpoint.

The incidence and rate (nocturnal or 24 hours) of all hypoglycemic events will be analyzed for the hypoglycemia categories of severe, documented symptomatic, asymptomatic, probable and relative, as defined in the publication of the ADA Workgroup on Hypoglycemia, 2015. These hypoglycemia categories will be analyzed as for nocturnal symptomatic hypoglycemia described previously.

The percentage of time plasma glucose in target range 70-140 mg/dL (3.9–7.8 mmol/L), the percentage of time plasma glucose <70 mg/dL (3.9 mmol/L), <54 mg/dL (3 mmol/L), the percentage of time glucose >140 mg/dL (7.8 mmol/L), >180 mg/dL (10 mmol/L) and > 250 mg/dL (13.9 mmol/l) will be calculated and summarized and analyzed as for the primary endpoint. For these endpoints, the time period of observation will be all evaluable time (24 hours) and nocturnal, where nocturnal is defined as the period between 00:00-05:59 within the evaluable assessment interval.

All other continuous CGM endpoints including the glucose variability parameters (MAGE, DT, AUC, CONGA-1, CONGA-2, CONGA-4) will be summarized, and will be analyzed using the same model as described for the primary endpoint.

The absolute values, each post-prandial to pre-prandial excursion and change in 7-point SMPG profiles (pre-prandial and 2-hour post-prandial plasma glucose at breakfast, lunch and dinner, and bedtime) from baseline to Week 12, Week 16 and the last on-treatment value (study endpoint) will be presented descriptively by treatment group.

Summary statistics will also be presented for the absolute values and the change from baseline in HbA1c and central lab FPG to Week 8, Week 16 and last on-treatment value (study endpoint). The change from baseline to study endpoint will be analyzed using a mixed-effect model with repeated

measures (MMRM) approach under the missing at random framework, using an adequate contrast at endpoint. The model will include fixed categorical effects of treatment arm, visit, treatment-by-visit interaction, randomization strata, and baseline HbA1c as covariate as well as baseline HbA1c-by-visit interaction.

Median, the first and the third quartiles and 10% and 90% percentiles of the curves, which are used to calculate the primary endpoint and secondary CGM endpoints, will be plotted for each treatment group.

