7.2.2 Exclusion criteria related to diabetes history and treatment

- E 13. Patients with type 2 diabetes mellitus,
- E 14. HbA1c \leq 6.5% or \geq 10% measured by the central lab test at Visit 1,
- E 15. Patients with fasting c-peptide ≥ 0.3 nmol/l as per source document or central lab test at Visit 1,
- E 16. Patients experienced none episode of documented symptomatic and/or severe hypoglycemia (as per the ADA classification) during the month prior to screening,
- E 17. Patients experienced > 1 episode of severe hypoglycemia resulting in coma/seizures in the last 12 months before screening,
- E 18. Patients receiving less than 1 year of treatment with basal plus mealtime insulin,
- E 19. Using any basal insulins other than the long-acting insulin analogs (i.e. Lantus, Toujeo, Levemir or Tresiba) in the past 3 months before screening,
- E 20. Requiring >80 U/day basal insulin analogs within 30 days prior to screening,
- E 21. Not on stable dose of basal insulin analogs (20% total dose) within 30 days prior to screening,
- E 22. Using human regular insulin as mealtime insulin within 30 days prior to screening,
- E 23. Using less than 2 injections of rapid-acting insulin analog within 30 days prior to screening,
- E 24. Using an insulin pump in the last 6 months before screening,
- E 25. Initiation of any glucose-lowering agents in the last 3 months before screening,
- E 26. Weight change of \geq 5 kg in the last 3 months before screening.

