10.1.1.2 Visit 2 (Week -3)

Visit 2 will occur about 1 week after Visit 1 when the investigator has received laboratory reports for the screened patients in order to assess Exclusion E14 and E15 (Section 7.2).

At this visit, patients will be trained with the blinded CGM performance. During the training the purpose of blinded CGM, the duration of CGM conduct, the requirement of daily calibration with SMPG and how to handle the device will be thoroughly explained and all questions be answered (Section 10.2.4). After the training, the patients will perform CGM sensor insertion under the supervision of the investigator or the study staff. Patients will stay at the study site for 2 more hours to complete the first calibration process and to receive additional training if needed. All patients will be instructed to wear the CGM device for 7 consecutive days.

Furthermore, following will be assessed:

- Changes from BID to QD Lantus injection and/or the injection time to morning injection from any other time (if applicable),
- Compliance with SMPG performance and at least 5 days of 5-point SMPG during the next week for randomization eligibility will be enforced. (Section 7.2.4),
- Any AE/SAE, including hypoglycemia since Visit 1 for eCRF documentation,
- Schedule for Visit 3 should include one day to perform the 7-point SMPG.

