11.4.2.2 Analysis of secondary efficacy endpoint(s)

Nocturnal symptomatic hypoglycemia will be defined as an event with typical symptoms of hypoglycemia accompanied by SMPG \leq 70 mg/dL (3.9 mmol/L) that occurs between 00:00 and

05:59 hours. The incidence will be analyzed using logistic regression, adjusting for randomization strata and other baseline characteristics (duration of diabetes, BMI and age) as clinically appropriate and if the model permits.

The rate per patient-year of nocturnal symptomatic hypoglycemic events will be analyzed using an over-dispersed Poisson regression model, adjusting for randomization strata and other baseline characteristics (duration of diabetes, BMI and age) as clinically appropriate and if the model permits.

The percentage of time glucose concentrations obtained by CGM within the target range of 70-140 mg/dL (3.9-7.8 mmol/L) during the last 4 hours of CGM data prior to the next day basal insulin injection will be calculated as the total time within that time period that the plasma glucose is in the range, divided by the length of that time period of observation.

The period of observation for the calculation will comprise of the last 4 hours during the final evaluable 24-hour period, where the evaluable period is defined as for the primary endpoint.

Total, within day and between day coefficient of variation (calculated for each period as the ratio of the standard deviation of the glucose values to mean of the glucose values).

Both the percentage of time glucose concentrations within the target range of 70-140 mg/dL (3.9-7.8 mmol/L) and the total, within day and between day coefficient of variation will be summarized at baseline and study endpoint by treatment group using mean, median, standard deviation, minimum and maximum, and will be analyzed as for the primary endpoint.

Other endpoints

The frequency and rates (nocturnal or 24 hours) of all hypoglycemic events will be analyzed for the hypoglycemia categories of severe, documented symptomatic, asymptomatic, probable and relative, as defined in the publication of the ADA Workgroup on Hypoglycemia, 2015. These hypoglycemia categories will be analyzed as for symptomatic hypoglycemia described previously.

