1 OVERVIEW AND INVESTIGATIONAL PLAN

1.1 STUDY DESIGN AND RANDOMIZATION

This is a multicenter, randomized, active-controlled, parallel group, 16-week open-label study. The study consists of an up to 4-week screening and Continuous Glucose Monitoring (CGM) training period and a 16-week treatment period (simple titration versus carbohydrate counting).

Patients satisfying the inclusion/exclusion criteria and CGM requirements are randomized 1:1 to morning injection of either Toujeo or Lantus. The randomization is stratified by baseline HbA1c (<8%, ≥8%), frequency of Lantus insulin injections at screening BID vs QD, current CGM use (yes/no) and mealtime insulin titration algorithm.

Approximately 616 patients are randomized, aiming for approximately 524 patients with evaluable data.

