2.1.3.2.1 Hypoglycemia

2.1.3.2.1.1 Hypoglycemia classification

Hypoglycemia observation periods

- **Pre-treatment hypoglycemia events** are events that occur during the pre-treatment period
- **Treatment-emergent hypoglycemia events** are events that occur during the on-treatment period
- **Post-treatment hypoglycemia events** are events that occur during the post-treatment period

Hypoglycemia events will be categorized as defined in [Appendix A](#). The glucose values used to classify hypoglycemia events are from the hypoglycemia e-CRF rather than the glucose values from CGM or central laboratory.

The incidence (proportion of patients with any hypoglycemia events) and the rate (number of events per patient year of exposure) will be assessed during each safety observation period for each hypoglycemia category.

In case of some classification items are missing (i.e. assistance required or not, presence of symptom, glycemic values, use of countermeasure) to determine hypoglycemia classification (see Section 2.5.3) the following categories will be presented.

- Not classified – non severe
- Not classified – severity unknown

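### The model for the nocturnal hypoglycemia rate omits each patient's pre-treatment hypoglycemia, which is already recorded, and so gives up some precision on that endpoint

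*SAP*

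**What the plan says.** **Rate model.** SAP 2.4.4.2 analyses nocturnal symptomatic events per patient-year "using an over-dispersed Poisson regression model, adjusting for randomization strata and other baseline characteristics (duration of diabetes, baseline BMI and age"), if the model permits. Protocol 11.4.2.2 has the same set: "using an over-dispersed Poisson regression model, adjusting for randomization strata and other baseline characteristics (duration of diabetes, BMI and age").

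**Incidence model.** SAP 2.4.4.2: the proportion with any event "will be analyzed using logistic regression, adjusting for randomization strata and other baseline characteristics (duration of diabetes, baseline BMI and age"). A log-binomial model for the risk ratio uses the same covariates.

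**Primary model, for contrast.** SAP 2.4.4.1 adjusts for "duration of diabetes, baseline BMI, age and baseline value) and randomization strata if model permits". CGM endpoints analysed with that model therefore carry a baseline value.

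**Strata.** SAP 1.1 lists HbA1c, basal injection frequency, "current CGM use (yes/no) and mealtime insulin titration algorithm". None concerns hypoglycemia.

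**Entry.** Exclusion E 16 (Protocol 7.2.2) removes "Patients experienced none episode of documented symptomatic and/or severe hypoglycemia" in the month before screening. Everyone enrolled thus has at least one such episode, at any hour, and the documents cap only severe episodes with coma or seizures (E 17).

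**Recording before treatment.** Only the study meter is used after Visit 1 (Protocol 10.2.3), and all episodes go on a dedicated e-CRF form (10.2.3.1). Visit 2 collects "Any AE/SAE, including hypoglycemia since Visit 1 for eCRF documentation" (10.1.1.2). SAP 2.1.3.2.1 defines pre-treatment hypoglycemia events, which "are events that occur during the pre-treatment period", and assesses incidence and rate in each observation period.

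**Place in the testing order.** SAP 1.3 calls the nocturnal rate the key secondary endpoint and claims at least 80% power at a rate ratio of 0.86. In SAP 2.4.4.3 incidence is tested first after the primary endpoint and the rate second.

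**The concern.** A patient's recent event count is a natural predictor of later events. Some patients will have had one qualifying episode and others many, and stable differences of this kind feed the over-dispersion that widens the standard error of the rate ratio. The plan already collects and classifies the screening events, and it uses a baseline value for the CGM endpoints, but it does not use one here. What is at stake is the width of the confidence interval and the power for the rate. The power claim gives neither a control rate nor a dispersion, so how much margin this endpoint has is unknown.

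**Working it through.** **1. The plan's own figure.** With T = 262 × 16/52 = 80.6 patient-years per arm, control rate λ and dispersion φ,

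Var(log RR) = φ × [1/(λT) + 1/(0.86 λT)] = 2.163 φ/(λT).

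For 80% power at two-sided 5%, the variance must be (0.1508/(1.960 + 0.842))² = 0.002898. So λ = 2.163 φ/(80.6 × 0.002898) = 9.26 φ per patient-year, or 9.26 × 80.6 × 1.86 ≈ 1,388 φ events in total. Without λ and φ the stated 80% can be neither reproduced nor refuted:

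| Control rate per patient-year | Power, φ = 1 | Power, φ = 2 |
|---|---|---|
| 5 | 54% | 31% |
| 10 | 83% | 54% |
| 20 | 99% | 83% |

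**2. What E 16 does to heterogeneity.** Take a gamma frailty with mean 1 and variance v, fully stable over time, and require at least one event in a month. All-hours rates of 4 × 3 = 12 to 4 × 8 = 32 per year give m = 1 to 2.67 expected events a month. For v = 1, m = 1:

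- P(at least one event) = 1 − 1/2 = 0.5
- mean among those selected = (1 − 1/4)/0.5 = 1.5
- second moment = (2 − 2/8)/0.5 = 3.5
- squared coefficient of variation = 3.5/1.5² − 1 = 0.56

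Over m = 1 to 2.67 the squared coefficient of variation falls from 1 to 0.56–0.66, and from 2 to 0.82–1.04. Entry selection therefore has to be part of the calculation.

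**3. Gain with the selection applied.** The simulation used 262 per arm, rate ratio 0.86, 16 weeks and a quasi-Poisson fit with and without log(screening count + 0.5). Assumptions, none given in the documents: nocturnal rate 3–8 per patient-year; all-hours rate 4 times nocturnal; frailty variance 1–2 before selection; 2–4 screening weeks; event-proneness only partly shared between screening and treatment. The variance of the log rate ratio fell about 2–22%.

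- Standard error: √0.98 = 0.990 and √0.78 = 0.883, so 1–12% smaller.
- Equivalent sample size: 1/0.98 = 1.02 and 1/0.78 = 1.28, so like 2–28% more patients.
- Illustration at λ = 5, φ = 2: SE = √(2 × 2.163/(5 × 80.6)) = 0.104 and 0.1508/SE = 1.456, power 31%. Dividing 1.456 by 0.990 or 0.883 gives 1.471 or 1.649, power 31% or 38%.

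**4. A second simulation, without the E 16 selection.** Lognormal patient rates, correlated between screening and treatment; control nocturnal rate 2, 5 or 10; variance 1–2; 2–4 screening weeks; correlation 0.5–0.8; counts either nocturnal or 24-hour (8 times nocturnal).

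- Rate model: model standard error 1–27% lower, power change about −1 to +17 points. At rate 5, 3 weeks, variance 1.5 and correlation 0.8, it went from 0.128 to 0.117 with nocturnal counts and to 0.104 with 24-hour counts. In the 24-hour case the empirical standard deviation fell less, from 0.127 to 0.108 (15%, against 19% for the model standard error).
- Correlation 0: 0.114 before and after, so no gain.
- Logistic incidence model: the standard error did not fall (0.178 to 0.188 in the 24-hour case). Power changed by about −2 to +5 points as the estimate moved away from zero.
- Rate ratio 1: rejection 0.05–0.06 for both endpoints.

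**The case against.** **The plan is valid as it stands.** Leaving a prognostic covariate out of a randomized comparison does not bias the rate ratio, and chance imbalance is already allowed for in the standard error. This stands in full.

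**A gain on the rate counts for formal inference only if the primary and the incidence tests both succeed.** This stands too. The rate ratio and its interval will still be reported and read whatever the order.

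**The gain rests on assumptions, some of them favourable.** Neither simulation, as described, includes the covariates already planned (diabetes duration, HbA1c stratum, CGM use), which may explain part of the heterogeneity. Persistence of event-proneness is assumed. This stands, and it is why only a range can be given.

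**Screening is a poor baseline window.** It is short, varies in length and includes the switch to once-daily morning dosing (Protocol 8.2.3.1 and 10.1.1.1), and patients enter on different basal analogs. Its correlation with on-treatment events may be weak. That limits the gain, but a weak covariate costs the rate model little.

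A reader might also infer that precision is lost on both hypoglycemia endpoints. The check does not support this, since the logistic standard error does not fall. Nor does the omission show the 80% power claim to be wrong, because the documents do not give what is needed to test it.

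**Conclusion.** The gap is real: a baseline value that is already collected is missing from the model for the key secondary rate endpoint. The consequence is lost precision on that one endpoint, without bias or type I error inflation.

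Under the assumptions in step 3 of the working, with E 16 applied, adjustment lowers the variance of the log rate ratio by roughly 2–22%. The figure depends heavily on how far event-proneness carries over from screening to treatment, and it is zero if the two are uncorrelated.

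A reader could take a larger figure from the simulation without E 16, where a 27% lower standard error means 1 − 0.73² = 47% lower variance. That case pairs a high rate with strong correlation in an unselected population, and the documents support neither input. This is a cheap improvement in efficiency, not a flaw that threatens the trial's conclusions.

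**What to change.** In SAP 2.4.4.2, prespecify one further covariate for the over-dispersed Poisson model:

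log((all-hours documented symptomatic events from Visit 1 to first IMP dose + 0.5) / screening days).

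All-hours counts are preferable because nocturnal counts over a few weeks will be sparse. The constant handles zero counts, and the divisor handles unequal screening lengths. With equal lengths the divisor only shifts the intercept, so the covariate matches the one simulated.

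State that the other hypoglycemia rate models that reuse this model, in SAP 2.4.4.2 and in the safety repeat in 2.4.5.3, take the same covariate. Adding it to the logistic incidence model is optional: power changes by about −2 to +5 points, and the conditional odds ratio shifts. Because the trial is open-label, the change should be fixed before any comparison by arm is seen.

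The cost is a short SAP edit and one derived variable, with no new data. The downside is one more covariate, measured in a short window that includes the switch to once-daily morning dosing. The rate ratio keeps its meaning.
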